7.2 Safety profile and management of AEs for IMPs

AEs will be collected from the first study-mandated procedure until the End of Study visit to be done 28 days (± 3 days) after the last day of study treatment. All study subjects/patients will be carefully monitored for the occurrence of AEs during this period.

Clearly related signs, symptoms and abnormal diagnostic procedure results should be grouped together and reported as a single diagnosis or syndrome whenever possible. Any additional events that fall outside this definition should also be reported separately.

All AEs must be recorded in the CRF. The investigator should follow each adverse event until the event has resolved to baseline grade or better, the event is assessed as stable by the investigator, the patient is lost to follow-up, or the patient withdraws consent. Every effort should be made to follow all serious adverse events considered to be related to study drug or trial-related procedures until a final outcome can be reported.

Table 5. Guidelines for Management of Patients Who Experience Adverse Events Associated with Giredestrant (GDC-9545).

Adverse Reaction	Event action to be taken
Elevation of hepatic transaminases	
General guidance	
 If patient presents with jaundice, coagulopathy, abdominal pain, or other symptoms suggestive of hepatic toxicity, perform liver function tests with additional evaluation per institutional guidelines. If hepatic enzymes are elevated with no obvious malignant cause found, consult with hepatologist. Treat patient with hepatic enzyme elevation according to local standard of care.
Grade 1 or 2	
 Continue giredestrant (GDC-9545). Rule out alternative etiologies (e.g., disease progression, concomitant medications, or biliary obstruction). Treat patient according to local standard of care.
Grade 3	
 Permanently discontinue giredestrant (GDC-9545). Consult with hepatologist.
Grade 4 or meets criteria as defined by Hy's Law*	
 Permanently discontinue giredestrant (GDC-9545). Consult with hepatologist.
Gastrointestinal events (nausea, vomiting, diarrhea)	
General guidance	
 Monitor closely for GI symptoms. If patient presents with nausea, vomiting, or diarrhea, manage according to local standard of care, including use of anti-diarrheal agents and supportive care such as hydration and dietary modification as appropriate. Infectious or alternate etiologies should be ruled out.
Grade 2	
 Manage and treat according to local standard of care. If persistent despite appropriate medical therapy, withhold giredestrant (GDC-9545) until resolution to Grade ≤ 1.
Grade ≥ 3	
 Withhold giredestrant (GDC-9545) until event resolves to Grade ≤ 1. Manage and treat patient according to local standard of care. Consider consulting with gastroenterologist. Resume giredestrant (GDC-9545) at full dose once the event resolves to Grade ≤ 1. If adverse event is recurring and patient cannot tolerate treatment, then permanently discontinue giredestrant (GDC-9545).

Adverse Reaction	Event action to be taken
Venous thromboembolic events (including pulmonary embolism)	
General guidance	
 Advise patient to seek immediate medical attention if they become aware of any symptoms of PE or DVT, such as acute onset of chest pain, shortness of breath, or swelling in extremities.
Grade ≥ 2	
 Withhold giredestrant (GDC-9545) until patient is stable. Manage and treat patient according to local standard of care. Resume giredestrant (GDC-9545) at full dose once the patient is stable. Permanently discontinue giredestrant (GDC-9545) for recurrent thromboembolic events.
Bradycardia	
General guidance	
 Monitor patient closely for symptomatic bradycardia.
Grade 1	
 Continue giredestrant (GDC-9545). Continue to monitor patient per schedule of activities. If heart rate falls below 40 bpm, withhold giredestrant (GDC-9545) until heart rate returns to > 40 bpm and patient remains asymptomatic.
Grade 2	
 Withhold giredestrant (GDC-9545) and consult with cardiologist. Resume giredestrant (GDC-9545) at full dose once the event improves to Grade ≤ 1 and the heart rate returns to >40 bpm. For recurrent Grade 2 bradycardia, permanently discontinue giredestrant (GDC-9545).
Grade ≥ 3	
 Permanently discontinue giredestrant (GDC-9545) and consult with cardiologist.
Renal toxicity or increased creatinine	
Grade 1 or 2	
 Continue giredestrant (GDC-9545). Manage patient according to local standard of care.
Grade ≥ 3	
 Permanently discontinue giredestrant (GDC-9545). Manage patient according to local standard of care. Consult with nephrologist.
Non-hematologic toxicity	
Grade 1 or 2	
 Continue giredestrant (GDC-9545). Rule out alternative etiologies.
Grade 3	
 Withhold giredestrant (GDC-9545) until symptoms resolve to Grade ≤ 1, and then resume giredestrant (GDC-9545) at full dose.
Grade 4	
 Permanently discontinue giredestrant (GDC-9545).

DVT = deep vein thrombosis; GI = gastrointestinal; PE= pulmonary embolism; ULN = upper limit of normal.

*The finding of an elevated ALT or AST ($> 3 \times \text{ULN}$) in combination with either an elevated total bilirubin ($> 2 \times \text{ULN}$) or clinical jaundice in the absence of cholestasis or other causes of hyperbilirubinemia is considered to be an indicator of severe liver injury (as defined by Hy's Law).

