9. **AE reporting:** After informed consent has been obtained but prior to initiation of study drug, only serious adverse events caused by a protocol-mandated intervention should be reported with grading according to the NCI–CTCAE v.5.0 criteria. After initiation of study drug, all adverse events will be reported until 28 days (EoS) after the final dose of study treatment. After this period, the Sponsor should be notified if the investigator becomes aware of any serious adverse event that is believed to be related to prior study drug treatment.
10. **Concomitant medication reporting:** Medication (e.g., prescription drugs, over-the-counter drugs, vaccines, herbal or homeopathic remedies, nutritional supplements) used by a patient in addition to protocol-mandated treatment from 14 days prior to initiation of study drug until end of study visit.
11. **12-lead ECG:** Patients should be resting in a supine position for at least 10 minutes prior to ECG recording. All ECGs will be obtained prior to other procedures scheduled at that same time (e.g., vital sign measurements, blood draws). All patients must have a standard 12-lead ECG in screening period, maximum 48h before start of treatment dose, in the EoT visit and in the EoS visit.
12. **Laboratory assessments:** These values should include: hematological test (hemoglobin, hematocrit, red blood cell count, platelet count, WBC and differential count [ANC, lymphocytes, monocytes, eosinophils and basophils, and other cells]); coagulation (INR, PTT (or aPTT)); chemistry panel (serum or plasma): sodium, potassium, chloride, glucose, BUN or urea, creatinine, total protein, albumin, phosphate, calcium, total bilirubin (if total bilirubin is 2xULN, also direct bilirubin), AST, ALT, ALP, urate and LDH; fasting lipid panel: cholesterol, LDL cholesterol, HDL cholesterol, and triglycerides (after ≥ 8 hours of fasting); urinalysis, including dipstick (pH, specific gravity, glucose, protein, ketones, and blood) and microscopic examination (sediment, RBCs, WBCs, casts, crystals, epithelial cells, and bacteria), FSH and estradiol. Baseline (Day 1, prior to initiation of study treatment) laboratory assessments are not required if the screening assessments were performed at within 14 days prior to initiation of study treatment.

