1.5.2 Treatment Phase and End of Treatment visit

The treatment phase is defined as the time between the study entry and the last dose of study treatment received within this trial. After confirming eligibility through the screening process, patients will be scheduled for visit day 1 (D1) of treatment within 48 h after randomization.

In this first visit, medical history, including clinically significant diseases, surgeries, cancer history, and reproductive status will be recorded at baseline. In addition, all medications (e.g., prescription drugs, over-the-counter drugs, vaccines, herbal or homeopathic remedies, nutritional supplements) used by the patient within 7 days prior to initiation of study treatment will be recorded. Also, in this first visit D1, patients will be given the first dose of treatment and will be instructed how to take giredestrant or tamoxifen orally, daily at their homes during the following 14 days D2 to D15 (to finalize a total of 15 days of treatment).

To assess patient compliance with self-administration of study medication, site study staff will provide patients with detailed instructions and training for the handling and administration of study drugs. Patients will receive and should be instructed to complete a medication diary to record all relevant information during those days.

A second biopsy will be collected at the EoT (on day 15 or day 15 + 1), after last dose of study treatment is taken by the patient in the EoT visit. If a fresh post-treatment biopsy cannot be obtained within + 1 day from last day of treatment, treatment will be extended to 16 days and patients will be able to have surgery or biopsy the following day (be it D15 + 2 days).

If a mandatory procedure described in the protocol falls on a bank holiday and/or weekend, this procedure should be performed on the day before or after the holiday (i.e. within a period of ± 2 working days), with the exception of the post-treatment surgery or biopsy that must be performed on the last day of treatment or 1 day after last day of treatment.

All patients will be closely monitored for safety and tolerability during study treatment. Patients should be assessed for toxicity prior to any study treatment administration; dosing will occur only if the clinical assessment and local laboratory test values are acceptable.

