4.5.2 Adverse Events

The adverse events will be tabulated per arm containing the number and percentage of subjects with the following:

- Subjects with at least one Adverse Event; and number of reported adverse events
- Subjects with at least one AE of special interest (AESI); and number of AESI
- Subjects with at least one Serious Adverse Events (SAEs); and number of SAEs
- Subjects with at least one AE related to the treatment; and number of AE related to the treatment
- Subjects with at least one SAE related to the treatment; and number of SAE related to the treatment

- Subjects who died due to SAEs; and number of SAEs that caused death
- Subjects that dropout due to SAEs; and number of SAEs that caused discontinuation
- Subjects with at least one treatment-emergent adverse event (TEAE); and number of reported TEAE. Adverse events starting or worsening during treatment phase will be considered as TEAEs.
- Subjects with at least one TEAE Grade ≥ 3 ; and number of reported TEAE Grade ≥ 3 .

The AEs will be also summarized according to the primary SOC and within each SOC, by PT according to the Medical Dictionary for Regulatory Activities (MedDRA). The duration of AE will be calculated as follows:

- Duration of an AE (days): (*date of resolution*) – (*start date*) + 1 when both end and start dates of AE are known and complete.

Missing data imputation methods

When data is not completed it will be considered as:

- Day 15 if day is missing
- Day 1 and month July if day and month are missing

In the event of not being able to allocate an AE, it will be considered as being a TEAE. Any missing information will be considered as being the worst case scenario (serious and treatment related).

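### Protocol 7.2 and Appendix 1 note 9 give different rules for collecting adverse events before the first dose, and the SAP's AE tables have no first-dose cut, so the level of AE incidence depends on which rule a site follows

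*Protocol*

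**What the plan says.** **Protocol 7.2** sets the collection window: "AEs will be collected from the first study-mandated procedure until the End of Study visit". It adds that "All AEs must be recorded in the CRF", with no exception for the time before dosing. Protocol 7.2.1 likewise has the investigator record all adverse events on the AE eCRF and report them to the sponsor.

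**Protocol Appendix 1, note 9** sets a narrower rule. Between consent and the start of study drug, "only serious adverse events caused by a protocol-mandated intervention should be reported". The full duty begins later: "After initiation of study drug, all adverse events will be reported until 28 days (EoS) after the final dose of study treatment".

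**SAP 2.4** names incidence and severity of AEs as a secondary endpoint. **SAP 4.5.2** tabulates "Subjects with at least one Adverse Event; and number of reported adverse events", then SAEs, then AEs by SOC and PT. None of these outputs is restricted by onset date. The safety set in SAP 3 requires at least one dose, which selects patients and not events.

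**TEAE rows.** SAP 4.5.2 also has TEAE rows: "Adverse events starting or worsening during treatment phase will be considered as TEAEs". SAP 1.5.2, like Protocol 3.3.2, defines that phase: "The treatment phase is defined as the time between the study entry and the last dose of study treatment received within this trial". SAP 6, on changes from the protocol, is marked as not applicable.

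**The concern.** Both collection rules stand in the current protocol version and nothing says which prevails. A woman with a mild cold and a haematoma from a study-mandated biopsy during screening, and nothing after dosing, has two AEs under 7.2 and none under note 9. The SAP would count both events and place her among subjects with at least one AE if the site followed 7.2, and would count nothing if the site followed note 9.

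The level of a secondary endpoint is therefore partly a matter of site practice. Drug-free time can enter the any-AE and SOC/PT tables, and sites are not comparable. An added background count common to both arms also narrows any real difference in the proportion of subjects with an AE.

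**Working it through.** The plan gives no figure to reproduce. The check is a comparison of passages, followed by a scale calculation.

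**1. Where the two collection rules differ (before the first dose)**

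| Pre-dose event | Protocol 7.2 | Appendix 1 note 9 |
|---|---|---|
| SAE caused by a protocol-mandated intervention | in | in |
| SAE not caused by one | in | out |
| Non-serious AE, procedure-related or not | in | out |

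Reading collection and reporting as separate duties does not remove the conflict. Section 7.2 requires every AE in the CRF, and the SAP counts reported AEs.

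**2. Whether the TEAE rows repair it**

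Study entry is not tied to a date. If it means consent, screening events count as treatment-emergent. If it means randomization, at most about 48 hours of pre-dose time is included, because Day 1 falls within 48 h of randomization. SAP 1.5 (a 15-day treatment phase separate from screening) and the columns of Protocol Appendix 1 (treatment period starting at Day 1) suggest a Day 1 start. At the other end, the phase stops at the last dose, so read literally it omits new events in the 28-day follow-up. SAP 4.5.2 adds that "In the event of not being able to allocate an AE, it will be considered as being a TEAE". The rows therefore help on one reading and not on another.

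**3. Window lengths** (screening up to 28 days, treatment 15 days, EoS 28 days after last dose)

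- Day 1 to EoS: 15 + 28 = 43 days.
- Maximum under 7.2: 28 + 43 = 71 days, a ratio of 71/43 = 1.65. The pre-dose share is 28/71 = 39%.
- With the ±3 day EoS window and the 16-day extension, the ratio runs from 1.60 to 1.70 and the share from 37% to 41%.
- With 14 pre-dose days: 57/43 = 1.33, a share of 14/57 = 25%.

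**4. Effect on subjects with at least one AE** (assumed constant background rate r per 28 days; the documents give none)

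P = 1 − exp(−r × days/28)

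| r | 43 days | 57 days | 71 days |
|---|---|---|---|
| 0.1 | 14% | 18% | 22% |
| 0.2 | 26% | 33% | 40% |
| 0.4 | 46% | 56% | 64% |

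**5. Effect on an arm difference** (assumed post-dose incidence 20% vs 35%, r = 0.2, every site following 7.2)

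- 28 pre-dose days: P(pre-dose AE) = 1 − exp(−0.2) = 0.181. The arms become 1 − 0.80 × 0.819 = 34.5% and 1 − 0.65 × 0.819 = 46.8%. The difference is 15.0 × 0.819 = 12.3 points.
- 14 pre-dose days: P = 1 − exp(−0.1) = 0.095. The difference is 15.0 × 0.905 = 13.6 points.
- For comparison, the standard error of 20% vs 35% with 46 per arm is √[(0.20 × 0.80 + 0.35 × 0.65)/46] = 9.2 points, so a 95% interval is about ±18 points.

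**The case against.** The best defence accepts that the two passages differ and disputes the consequences.

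- **Related AEs.** A reader might infer that pre-dose events inflate the related-AE rows. Protocol 7.1 defines relatedness by temporal association with the IMP, so a pre-dose event should not be judged related. Only missing causality, which SAP 4.5.2 sets to the worst case, could put one there. This objection stands.
- **Bias between arms.** A reader might infer that uneven site practice biases the comparison. Day 1 falls within 48 h of randomization, so nearly all pre-dose events precede allocation and are balanced in expectation. Only chance imbalance remains. This stands too.
- **Descriptive analysis and TEAE rows.** The SAP describes AEs by arm with no planned between-arm test, and shows treatment-emergent rows beside the any-AE rows. It is therefore too strong to say that drug-free time is simply presented as drug toxicity. But the endpoint is worded in terms of AEs, and the TEAE start is unclear, so these rows do not close the gap.
- **Length of the window.** Standard-of-care tests done before consent may be reused, and a diagnostic biopsy up to 8 weeks old may serve as baseline. The first study-mandated procedure can thus fall well after day −28. This stands: 28 days is a ceiling.
- **Definition of an AE.** Protocol 7.1 refers to a patient who has been given a product, which leans toward note 9. Section 7.2 nevertheless starts collection at the first procedure in express terms, so this is a further reason to reconcile the text.
- **Listing all AEs beside TEAEs is legitimate.** It is, provided the plan says which rows deliver the endpoint and when TEAE starts and ends. At present it does not.

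**Conclusion.** The inconsistency is real and the SAP does not resolve it. What depends on site practice is the level of the any-AE row and the SOC/PT tables, plus any pre-dose SAE not caused by a procedure in a woman who was later dosed.

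The firm part of the size is the window: at most about 28 extra days against 43, often fewer. The rest rests on assumed rates. With 28 pre-dose days, any-AE incidence from background events alone would rise from 14% to 22% at 0.1 AEs per 28 days and from 46% to 64% at 0.4. Dilution of the arm difference is modest. The fall from 15.0 to 12.3 points needs the full 28 days and the 7.2 rule at every site. With 14 days it is 13.6, and either shift is small beside a sampling error of about ±18 points.

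The documents do not support a claim of systematic bias between arms or of inflated related-AE rows. The primary endpoint is not touched. The point is still worth correcting, because it makes a secondary endpoint comparable across sites at almost no cost.

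**What to change.** 1. **Protocol.** The sponsor reconciles section 7.2 and Appendix 1 note 9 so that both state the same pre-dose collection rule.
2. **SAP 4.5.2, endpoint tables.** Name the rows and SOC/PT tables that deliver the AE-incidence endpoint. State that they count events with onset or worsening on or after the first dose through the EoS visit.
3. **SAP 4.5.2, TEAE.** Define TEAE with the same start and end, in place of the reference to the treatment phase.
4. **Pre-dose events.** Put them in a separate listing.

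The cost is a protocol clarification and a few sentences in the SAP. The SAP change makes the tables comparable even where sites have already followed different rules, provided onset dates are recorded. The small downside is that pre-dose procedure-related events move from the main tables to a listing.

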7.2.1 AEs and SAE reporting and timeframe

Reporting requirements will comply with all EU safety reporting requirements as detailed in "Regulation (EU) No 536/2014 of the European Parliament and of the Council of 16 April 2014 on clinical trials on medicinal products for human use, repealing Directive 2001/20/EC".

The investigator is responsible for ensuring that all adverse events (see Section 7.1 for definition) are recorded on the Adverse Event eCRF and reported to the Sponsor in accordance with instructions provided in this section.

For each adverse event recorded on the Adverse Event eCRF, the investigator will make an assessment of seriousness, severity and causality.

During the study period, resolution of adverse events (with dates) should be documented on the Adverse Event eCRF and in the patient's medical record to facilitate source data verification.

The investigator or investigator's team will report all protocol defined SAEs and AESIs to the Sponsor (MEDSIR) no later than 24 hours of any site study team staff becoming aware of the event as follows:

- The full details of the SAE and/or AESI should be collected and fully documented using the SAE form and sent to MEDSIR.
- Follow-up information, copies of the results of any tests, the outcome of the event plus the investigator's opinion of IMP relationship to the SAE(s) and AESI(s), and other document when requested and applicable, will accompany the SAE form as available on the day of reporting or provided as soon as possible thereafter.
- The original SAE Report Form and the fax confirmation sheet from the Sponsor must be kept with the CRF documentation at the study site(s).

All SAE forms will be sent by the investigator or investigator's team to the Sponsor (MEDSIR) according to the reporting instructions provided by MEDSIR at the site initiation visit and filed in the Investigator's File.

All SAEs must be reported to Drug Safety Evaluation (DSE) Clinical Safety and Pharmacovigilance (CSPV) team address: [contact].

SAEs and AESIS will be followed until resolved, a stable outcome or baseline condition is reached, subject/patient is lost to follow-up or dies.

As Sponsor, MEDSIR will be responsible for ensuring that events are reported within the mandated timeframe to the EMA and other Competent Authorities, Institutional Review Boards /Institutional Ethics Committees (IRBs/IECs) and investigator(s), as necessary and in accordance with all applicable guidelines, approved directives, and regulations. All safety reporting local regulatory requirements will be followed.

7.2.2 Expedited reporting to Health Authorities, Investigators, IRBs, and IECs

To determine reporting requirements for single SAE cases, MEDSIR (as Sponsor) or its designee will assess the expectedness of these events using the following reference documents:

- Current IMP SmPC/IB.

MEDSIR (as Sponsor) or its designee will compare the severity of each event and the cumulative event frequency reported for the study with the severity and frequency reported in the applicable reference document.

Reporting requirements will also be based on the investigator's assessment of causality and seriousness, with allowance for upgrading by the Sponsor as needed.

Within 7 calendar days after being notified of the event, MEDSIR (as Sponsor) or its designee will report unexpected fatal or life-threatening events associated with the use of the study drug to the regulatory agencies and competent authorities, to the investigators and IRBs/IECs. MEDSIR (as Sponsor) or its designee will report other unexpected SAEs associated with the use of the study medication to the appropriate competent authorities (according to local guidelines), investigators, and central IRBs/IECs by a written safety report within 15 calendar days of notification. All safety expedited reports will be reported in accordance to all regulatory reporting obligations (including timelines) and local regulatory requirements.

